Exclusion criteria include: 1) meeting DSM-5 criteria for a history of or current psychotic or bipolar affective disorders, 2) current suicidal or homicidal ideation and intent, 3) a history of seizures and/or a seizure disorder per the judgement of the medical clinician, 4) severe, unilateral intimate partner violence in the past 6 months as defined by the Revised Conflict Tactics Scale, and 5) pregnancy or breastfeeding for women, 6) Acute alcohol withdrawal as indicated by CIWA-Ar scores  $>8$ , Attendance at therapeutic activities other than study sessions will be closely monitored using the Treatment Services Review, 7) any unstable or serious medical condition affecting the potential participant's ability to participate in the study, 8) Individuals with claustrophobia; tattoos above the shoulders; permanent eyeliner or permanent artificial eyebrows; cardiac pacemaker; metal fragments in eye, skin, or body, including shrapnel; heart valve replacement; brain clips; venous umbrella; current or former sheet-metal worker or welder; lifetime history of aneurysm surgery; lifetime history of seizures and/or epilepsy per the judgement of the medical clinician; intracranial bypass, renal, or aortic clips; prosthetic devices such as middle ear, eye, joint, or penile implants; joint replacements; non-removable hearing aid, neurostimulator, or insulin pump; shunts/stents; metal mesh/coil implants; metal plate/pin/screws/wires; or any other MRI contraindications as determined by the MRI technician at the time of scanning will not be eligible to participate in the neuroimaging component of the study, however individuals who meet inclusion/exclusion criteria for the medication component of the study but not the MRI portion will still be eligible to reenroll in and complete the medication/treatment phase.

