## **5.0 Number of Subjects**

100 couples will be enrolled (200 total participants).

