## 7.0 Recruitment Methods

Recruitment sites will include the Center for Drug and Alcohol Programs (CDAP) at MUSC, the Ralph H. Johnson VAMC Substance Treatment and Recovery (STAR) clinic, and other in state and out of state VA clinics (e.g., Savannah CBOC). CDAP, directed by [name], is an inpatient and outpatient addictions treatment facility with approximately 398 inpatient and 880 outpatient annual admissions. There were 1,279 new CDAP admissions in 2017 (~106/month) with the majority of patients (75-80%) seeking AUD treatment. The STAR clinic is directed by [name] and [name] (Co-I) is a Staff Psychologist in STAR. Consults for treatment are made directly to the STAR intake team. In 2017, STAR delivered 1,460 unique patient visits (682 AUD patients; 56 patients/month). An additional recruitment site will be the outpatient Ralph H. Johnson VAMC Couples and Family Clinic, directed by [name]. The Couples and Family Clinic received 433 and 408 unique patient intakes in 2016 and 2017, respectively. We need to enroll 2-4 couples per month to complete the study within the proposed timeline. No other studies are enrolling couples at the proposed recruitment sites. Thus, there should be no difficulty recruiting an adequate sample. Participants will also be recruited through IRB-approved flyers posted in (a) VAMC Women's Health Clinic, Primary Care Clinic, and Emergency Department; (b) affiliated community based outpatient clinics; and (c) MUSC treatment clinics. Finally, we will place advertisements on social networking sites (e.g., Craigslist, Facebook), in local newspapers, and television. Participants who refer others to the study will be compensated \$10 per randomized referral, allowing us to reach a wider pool of potential participating couples. Further, participants from past MUSC research studies who have consented to be contacted for future research studies will be recruited. These individuals will be referred to us via other MUSC researchers, or they may have indicated consent to be contacted about future research studies within their MUSC medical records. Our research team has successfully used these methods in previous and ongoing clinical trials among individuals and couples with AUD.

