
**Table 1. Assessment Instruments and Timeline**

Instrument	Purpose	BSL	Weekly	Week 6	Week 12	3M F/U	6M F/U
Demographics Form	Characterize sample	X					
Mini Mental Status Exam (MMSE) 	Screen for cognitive deficits	PRN					
Quick Structured Clinical Interview for DSM-5 Disorders	Assess DSM-5 psychiatric disorders	X					
Concomitant Medications Form	Assess concomitant medications	X	X	X	X	X	X
Time Line Follow-[name] (TLFB) 	Primary outcome: AUD	X	X	X	X	X	X
Penn Alcohol Craving Scale (PACS  )	Assess alcohol craving	X	X	X	X	X	X
Alcohol Use Disorders Identification Test (AUDIT) 	Assess alcohol problems	X		X	X	X	X
Alcohol Dependence Scale (ADS) 	Assess domains affected by AUD	X			X	X	X
Readiness to Change Questionnaire (SOCRATES  )	Assess readiness to change AUD	X		X	X	X	X
Clinical Institute Withdrawal Assessment of Alcohol-Revised (CIWA-Ar) 	Assess alcohol withdrawal	X	X			X	X
Traumatic Life Events Questionnaire (TLEQ) 	Assess Trauma History	X					
PTSD Checklist (PCL-C) 	Assess PTSD symptoms	X			X	X	X
Beck Depression Inventory-II 	Assess depression	X	X	X	X	X	X
Cognitive Emotion Regulation Questionnaire; CERQ-Short 	Assess emotion regulation	X			X	X	X

Dyadic Adjustment Scale-short form (DAS) 	Primary outcome: Relationship functioning	X	X	X	X	X	X
Infidelity Assessment 	Assess Infidelity	X			X	X	X
Revised Conflict Tactics Scale 	Assess intimate partner violence	X		X	X	X	X
Reasons for Violence Scale 	Assess reasons for partner violence	X			X	X	X
Treatment Services Review	Monitor service utilization		X	X	X	X	X
Helping Alliance Questionnaire, Therapist and Client Version 	Asses therapeutic alliance		X	X	X		
Treatment Adherence	Assess homework compliance		X	X	X		
History of Head Injuries	Assess fMRI eligibility	X			X		
Drinking goals	Assess treatment goals for alcohol	X					
Coping Questionnaire	Assess coping skills	X					
Marijuana Motives	Assess marijuana use	X					
Visual Analog Scale (VAS)	Asses alcohol craving	X			X		
Telehealth Questionnaire	Asses telehealth				X		
Psychological Stress Associated with COVID-19 Crisis Questionnaire	Assess stress related to COVID-19	X					

BSL=Baseline. F/U = Follow-Up. BP=Orthostatic Blood Pressure. BMI= Body mass index.

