## 11.0 Data Management and Statistical Analysis Plan

**General.** Baseline clinical and descriptive characteristics will be examined and compared between treatment groups using chi-square tests, Fisher's exact tests, t-tests, or Wilcoxon rank sum tests, as appropriate. Baseline characteristics that are significantly different between treatment groups will be included as model covariates. The primary analysis will focus on end-of-treatment (i.e., the final three weeks of the treatment phase) outcomes using an intent-to-treat framework.

**Randomization.** Both partners in each couple will be randomized to the same drug condition in a one-to-one manner utilizing a randomized permuted block design. In order to ensure that the treatment groups are balanced with respect to alcohol consumption (TLFB), a stratified randomization process will be used.

We plan to use REDCap and VA REDCap for data capture and management. REDCap (Research Electronic Data Capture) is a software toolset and workflow methodology for electronic collection and management of research and clinical trial data (Harris et al., 2008; Harris et al., 2007). REDCap provides secure, web-based flexible applications, including real time validation rules with automated data type and range checks at the time of entry. Exports are made available for several statistical packages including SPSS, SAS, SATA, R and Microsoft Excel. The system allows the research team to create and engage respondents using a variety of notification methods.

REDCap data dictionaries can be distributed for reuse at multiple institutions. A library of data dictionaries is made available for standards-based data collection forms and validated instruments (Obeid et al., 2012). The underlying database is hosted in a secure data center at MUSC/VA, a secure environment for data systems and servers on campus, and includes redundancy, failover capability, backups and extensive security checks. The system has several layers of protection including, user/group account management, "Data Access Groups" which allow data to be entered by multiple groups in one database with segmented user rights for entered data, audit trails for all changes, queries and reports, and Secure Sockets Layer (SSL) encryption.

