**Power and Sample Size.** This study is powered to detect moderate treatment group differences in percent days abstinent (PDA) and percent of days of heavy drinking (PDH), and relationship functioning as measured by the TLFB and DAS-7, respectively at end-of-treatment (weeks 9-12). Assuming 2-sided hypothesis testing and alpha levels of 0.05, we will have 80% power to detect treatment group differences with effect sizes of 0.6 in the presence of 30% attrition (n=70 couples) during the treatment phase. This approach is consistent with treatment group differences in PDA ( $d=0.59$ ) and PDH improvements ( $d=0.79$ ) in a prior ABCT trial (n=102), although we recognize that that trial compared individual therapy vs. ABCT (not ABCT  $\pm$  medication). In that study, PDA increased from  $34.98\% \pm 29.17\%$  to  $80.52\% \pm 27.75\%$  at the end of treatment in the ABCT group, and PDH decreased from  $56.83\% \pm 28.87\%$  to  $10.52\% \pm 22.16\%$  in the ABCT group. Incorporating an arcsine or other appropriate transformation to account for non-normality of these metrics will enable us to discern whether oxytocin enhances end of treatment PDA by an additional absolute 9% or greater (i.e., to 80.5% in the ABCT+ placebo group vs. 89.5% in the ABCT + oxytocin group) and whether oxytocin further decreases PDH by an absolute 6% or greater (i.e., to 10.5%

in the ABCT+ placebo group vs. 4.5% in the ABCT + oxytocin group). Another prior ABCT trial found that DAS-7 scores ( $21.1 \pm 6.7$ ) remain relatively constant throughout treatment. We will have 80% power to detect treatment group differences of 4 units of improvement in DAS-7 scores.

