### Inclusion/Exclusion Criteria.

#### *Inclusion criteria*

- 1) Male or female; any race or ethnicity; aged 18-75 years.
- 2) Able to provide informed consent and function at an intellectual level sufficient to allow accurate completion of the assessment instruments (> 26 on the Mini-Mental State Exam).
- 3) Married, cohabiting, or in a committed relationship for  $\geq$  6 months.
- 4) Identified Patients (IPs) must meet DSM-5 diagnostic criteria for current (i.e., past 12 months) alcohol use disorder (assessed via the MINI). Couples in which both partners meet diagnostic criteria for current AUD are eligible for participation.
- 5) Concurrent substance use disorders (e.g., marijuana) are acceptable provided that alcohol is the IP's primary substance of choice.
- 6) Participants taking psychotropic medications will be required to be maintained on a stable dose for at least four weeks before study initiation. This is because initiation or change of psychotropic medications during the course of the trial may interfere with interpretation of results.

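### Outside AUD treatment is not recorded at baseline on the form meant to track it, and covariates are chosen by a test of imbalance; prespecifying background treatment would be a cheap, modest gain in precision

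*Combined protocol and SAP*

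**What the plan says.** **Outside treatment.** Recruitment draws on clinics that treat addiction, among them a centre described in Section 7.0 as an "inpatient and outpatient addictions treatment facility". Within the exclusion list, Section 4.0 states that "Attendance at therapeutic activities other than study sessions will be closely monitored using the Treatment Services Review". This describes monitoring and sets no limit. The lists in Sections 4.0 and 12.0 do not restrict other AUD therapy.

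**Medication.** Section 12.0 says: "Participants taking psychotropic medications will be required to be maintained on a stable dose for at least four weeks before study initiation". AUD medication is not named anywhere as allowed or as excluded.

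**Timing of measurement.** In Table 1 the Treatment Services Review, whose purpose is "Monitor service utilization", is marked weekly, at weeks 6 and 12 and at both follow-ups. Its baseline cell is empty. The Concomitant Medications Form is marked at baseline and at every later point.

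**Covariates.** Section 11.0, under General: "Baseline characteristics that are significantly different between treatment groups will be included as model covariates". The model for Hypotheses 1 and 2 always includes baseline PDA, PDH and DAS-7. It also leaves room for further baseline characteristics that may be significant, without saying how they are to be judged. Randomisation is stratified on TLFB alcohol consumption. No section says how Treatment Services Review data enter any analysis.

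**The concern.** The trial asks what oxytocin adds to ABCT. Participants recruited through addiction clinics may already be in other AUD treatment or on AUD medication, and either could plausibly affect PDA and PDH. Two features of the plan make that background harder to handle.

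- Service use has no scheduled baseline record on the form meant for it. Service use recorded during treatment may itself respond to the study arm, so it is not safe as an ordinary covariate.
- A test of baseline difference is a poor way to choose covariates. It responds to the accident of allocation, whereas the benefit of a covariate comes from how strongly it predicts the outcome. A strong predictor that happens to be balanced, or moderately unbalanced, is left out by that rule and its precision is lost.

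At stake are some power and, in any single trial, a small shift in the estimate that depends on how background treatment happened to fall between the arms.

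**Working it through.** **1. The plan's design figure.** Section 11.0 claims 80% power for d = 0.6 with 70 couples after 30% attrition, two-sided alpha 0.05. With 35 per arm, power = Φ(d·√(n/2) − 1.96) = Φ(0.6 × √17.5 − 1.96) = Φ(0.55) = 70.9% (69.7% by the t-test). The stated 80% is reached with a one-sided test (80.7%) or with a baseline correlation of about 0.45, which the plan does not state. That is a separate matter; here it shows only that there is little power to spare.

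**2. Inputs the documents do not give (assumptions).**
- Prevalence of background AUD treatment: 10% to 50%.
- Its effect: 0.3 to 0.5 SD, with 0.8 SD as an extreme; or 5 to 15 PDA points, which is 0.18 to 0.54 SD on the SD of 27.75 in Section 11.0.
- Correlation of baseline with end-of-treatment drinking: 0.4.

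**3. Size of chance imbalance.** The SD of the difference in proportions is √(2p(1−p)/n). At p = 26% and n = 50 per arm this is √(2 × 0.26 × 0.74 / 50) = 0.088.
- The mean absolute gap, from the exact binomial distribution, is about 7 percentage points.
- A gap of 16 points or more, in either direction, occurs in about 9% of trials; 10 points or more in about 30%.

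**4. What the significance rule can miss.** The largest non-significant gap is about 1.96 × SD.

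| Per arm | p = 10% | p = 50% |
|---|---|---|
| 50 | 12 points | 20 points |
| 35 | 14 points | 23 points |

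For example, 17/50 against 9/50 (34% against 18%) gives Fisher p = 0.110 and chi-square p = 0.068, so the rule would not bring it in.

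**5. Shift in the estimate = gap × effect of background treatment.**
- Typical gap: 0.07 × 5 to 15 = 0.35 to 1.05 PDA points, which is 4% to 12% of the 9-point target in Section 11.0.
- The 17 against 9 case: 0.16 × 5 to 15 = 0.8 to 2.4 points, or 9% to 27% of the target.
- Largest non-significant gap, effects of 0.3 to 0.5 SD: about 0.04 to 0.12 SD, against the planned 0.6.

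For scale, the unadjusted standard error of the PDA difference at 35 per arm is 27.75 × √(2/35) = 6.6 points.

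**6. Operating characteristics.** Simulation, 6,000 runs per cell, baseline drinking always in the model and background treatment independent of it. Power for d = 0.6 at 35 per arm:

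| Prevalence, effect | Adjust only if significant | Always adjust | Gain (points) |
|---|---|---|---|
| 30%, 0.3 SD | 74.9% | 75.2% | 0.3 |
| 30%, 0.5 SD | 74.0% | 75.4% | 1.4 |
| 50%, 0.5 SD | 73.4% | 75.9% | 2.5 |
| 30%, 0.8 SD | 70.5% | 76.4% | 5.9 |

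Across 35 and 50 per arm, type I error was 4.4% to 5.0% with test-then-adjust and 4.5% to 5.3% with always adjusting. With a simulation error of about √(0.05 × 0.95 / 6000) = 0.3 points, neither shows inflation.

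**The case against.** The strongest reply is that chance imbalance under randomisation is not bias: the standard error already allows for it, and the type I error results agree. This stands. What remains is precision, and a conditional shift in the one trial that is run.

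Several stronger readings are tempting, and the documents do not support them.

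- *AUD medication is permitted.* The text permits stable psychotropic medication and is silent on AUD drugs. All that can be said is that they are neither named as allowed nor excluded.
- *All background treatment is recorded too late.* Medication is on a baseline form. The timing gap concerns services only. Even there, the recall window of the Treatment Services Review, and whether its first weekly use precedes the first dose, are not stated.
- *A covariate can enter only through a significant imbalance.* The primary model fixes baseline PDA, PDH and DAS-7 and leaves a second route for other characteristics. That route is vague, but it exists.
- *Imbalance goes uncorrected.* Stratification on drinking, and baseline PDA and PDH as covariates, absorb part of any effect already visible in the 60-day baseline TLFB. They capture less of a treatment begun late in that window or one whose benefit is still growing.
- *The estimate could move by a quarter of its target.* The 9% to 27% range comes from a gap that arises in about 9% of trials and ignores the baseline adjustment. The typical figure is 4% to 12%.

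Sections 12.0 and 14.0 also restrict recently started psychotropic medication, and withdraw participants who need to start it or need more intensive care. These rules limit some changes in background treatment, but not ordinary outpatient services.

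**Conclusion.** The point holds as a modest improvement in precision and clarity, not as a correction of bias. Outside AUD treatment is not excluded, the form meant to track it has no baseline assessment, and the stated covariate rule selects by chance imbalance. The further allowance in the primary model gives no clear rule to replace it.

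The cost is about 0 to 3 points of power for assumed effects of 0.3 to 0.5 SD at 30 to 50% prevalence, and about 6 points only at an assumed 0.8 SD. A typical imbalance shifts PDA by about 0.35 to 1.05 points. Type I error is unaffected. Both prevalence and effect are assumptions, since the documents give neither. The power figures treat background treatment as unrelated to baseline drinking; where the two are related, the fixed baseline covariates already recover part of the loss. The change is worth making because it is cheap and because the recomputed power leaves little margin.

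**What to change.** 1. In Section 11.0, replace the significance-test rule with a list of covariates fixed before unblinding and used whatever the observed imbalance. For the PDA and PDH models, add to the present baseline values two yes/no items for the person whose drinking is analysed: AUD medication at baseline, taken from the existing Concomitant Medications Form, and outside AUD treatment at baseline. Remove the open-ended allowance for further characteristics, or give it a rule.
2. Add the Treatment Services Review to the baseline column of Table 1 for couples yet to be enrolled, with a stated recall window; the 60 days used for the TLFB would be natural.
3. Report outside AUD treatment after randomisation by arm, and do not adjust the primary model for it.
4. State in the eligibility text how AUD medication is handled, so that the covariate has a clear meaning. What that position should be is for the investigators.

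**Cost.** A few minutes at baseline, two degrees of freedom and some wording. The gain is small if few participants have background treatment. For any couples already enrolled, baseline service use will be missing, and the plan must say how the covariate is handled for them; medication can still be prespecified for everyone.

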## **5.0 Number of Subjects**

100 couples will be enrolled (200 total participants).

## 6.0 Setting

All procedures will be conducted on the MUSC campus or in VA research offices. Procedures can also be conducted via telehealth.

## 7.0 Recruitment Methods

Recruitment sites will include the Center for Drug and Alcohol Programs (CDAP) at MUSC, the Ralph H. Johnson VAMC Substance Treatment and Recovery (STAR) clinic, and other in state and out of state VA clinics (e.g., Savannah CBOC). CDAP, directed by [name], is an inpatient and outpatient addictions treatment facility with approximately 398 inpatient and 880 outpatient annual admissions. There were 1,279 new CDAP admissions in 2017 (~106/month) with the majority of patients (75-80%) seeking AUD treatment. The STAR clinic is directed by [name] and [name] (Co-I) is a Staff Psychologist in STAR. Consults for treatment are made directly to the STAR intake team. In 2017, STAR delivered 1,460 unique patient visits (682 AUD patients; 56 patients/month). An additional recruitment site will be the outpatient Ralph H. Johnson VAMC Couples and Family Clinic, directed by [name]. The Couples and Family Clinic received 433 and 408 unique patient intakes in 2016 and 2017, respectively. We need to enroll 2-4 couples per month to complete the study within the proposed timeline. No other studies are enrolling couples at the proposed recruitment sites. Thus, there should be no difficulty recruiting an adequate sample. Participants will also be recruited through IRB-approved flyers posted in (a) VAMC Women's Health Clinic, Primary Care Clinic, and Emergency Department; (b) affiliated community based outpatient clinics; and (c) MUSC treatment clinics. Finally, we will place advertisements on social networking sites (e.g., Craigslist, Facebook), in local newspapers, and television. Participants who refer others to the study will be compensated \$10 per randomized referral, allowing us to reach a wider pool of potential participating couples. Further, participants from past MUSC research studies who have consented to be contacted for future research studies will be recruited. These individuals will be referred to us via other MUSC researchers, or they may have indicated consent to be contacted about future research studies within their MUSC medical records. Our research team has successfully used these methods in previous and ongoing clinical trials among individuals and couples with AUD.

College students ages 18-75 enrolled at area colleges and universities will be contacted from respective registrar lists (no participants will be recruited until an interinstitutional agreement is signed by the respective institution, submitted as an amendment to the MUSC IRB, and approved by the MUSC IRB). Potential participants will be sent a recruitment email that includes details about the study (e.g., time requirement, basic inclusion criteria, compensation), a link to the IRB approved screener, and contact information for the research team will be included in the email. Potential participants will also be contacted via phone.

Chart review and EPIC/VINCI lists will be used for recruitment; only individuals who have previously agreed to be contacted for research opportunities will be identified. The study team will use an IRB approved letter and script will be used to inform identified individuals about our study.

Participants will be recruited and enrolled from all 50 states. The protocol/NIH grant application was written pre-COVID 19, where we had various recruitment methods that included in-person collaboration with providers and clinics, as well as physical methods of recruitment (like flyering) from community locations (bars and clinics, etc). Since the COVID 19 pandemic, the climate of clinical trial recruitment has shifted drastically and reaching potential participants has moved almost fully virtual/digital. With the shift in recruitment methods, the market has become saturated throughout most of our social media outlets. We have also difficulty getting new methods of recruitment strategies/platforms approved by

MUSC/SC purchasing restrictions. Thus, the inclusion of participants out of state increases the pool of potential participants, helping to mitigate the impacts of COVID19.

Further, the inclusion of out of state participants allows us to enroll more veterans referred through the VA system, as Savannah CBOC is part of the RHJVA.

[figure not shown]
Also, out of state recruitment allows for a more diverse study sample. Recruitment of out of state participants will be accomplished through social media advertisements targeted at out of state areas. The advertisements will include our study screener. Study staff will connect with the potential participant based on the method of contact indicated by the participant on the screener. Our study contact information will also be provided should the participant not want to provide contact information for themselves.

